5.1.2. Treatment Assignment

After a subject has completed the necessary documentation of definitive CLL progression in the primary clinical trial (GS-US-312-0116) and has been confirmed to be eligible, the subject can be entered into this trial (Study GS-US-312-0117). In order to obtain a treatment arm allocation for a subject, a site representative will access the IWRS and supply the system with the required information.

Subjects will be assigned to either of the following treatment assignments with allocation based on the original primary study randomization:

Treatment Groups

Blinded Portion

- Arm A: Idelalisib + rituximab (Study GS-US-312-0116) ⇒high-dose idelalisib (300 mg BID) (Study GS-US-312-0117)
- Arm B: Placebo + rituximab (Study GS-US-312-0116)
 ⇒standard-dose idelalisib (150 mg BID) (Study GS-US-312-0117)

Open-Label Extension Portion (following unblinding)

- Arm A: subjects already on 300 mg BID will continue, and newly enrolled subjects will receive 150 mg BID
- Arm B: subjects already on 150 mg BID will continue, and newly enrolled subjects will receive 150 mg BID

Note: At the Investigator's discretion, subjects who were randomized to placebo on Study GS-US-312-0116 may delay initiation of idelalisib following enrollment on Study GS-US-312-0117 until the time of disease progression or until the investigator determines that the subject would benefit from initiation of idelalisib treatment.

Treatment Assignment

- Assignment to Arm A or Arm B with allocation based on the original primary study randomization
- Implementation through an interactive web response system (IWRS)

The IWRS will assign blister card, or bottle numbers and instructions for dispensing of blinded study drug (high-dose or standard-dose idelalisib). It is anticipated that subjects will usually begin study drug immediately at Visit 2 of the study.

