5.2. Investigational Study Drug (Idelalisib/Placebo)

5.2.1. Description

Subjects allocated to Arm A in the blinded portion of the study will be provided with 2 tablets of active idelalisib for oral administration at each dose. Each tablet contains 150 mg or 100 mg of active idelalisib. The 150-mg tablets will be used for initial therapy; the 100-mg tablets are provided for use by those subjects who require a dose reduction (see Table 5-1).

Subjects allocated to Arm B in the blinded portion of the study will be provided with 1 tablet of active idelalisib and 1 tablet of placebo for oral administration at each dose. Each active tablet contains 150 mg or 100 mg of active idelalisib. The 150-mg tablets (and matching placebo) will be used for initial therapy; the 100-mg tablets (and matching placebo) are provided for use by those subjects who require a dose reduction.

In the open-label portion of the study, subjects will be provided with 150 mg tablets of idelalisib.

The 150-mg tablets are pink, oval-shaped film-coated, and include the following inactive excipients: microcrystalline cellulose, hydroxypropyl cellulose, croscarmellose sodium, sodium starch glycolate, magnesium stearate, red iron oxide, polyethylene glycol, talc, polyvinyl alcohol (PVA), and titanium dioxide. The 100-mg tablets are orange, oval shaped film-coated, and include the following inactive excipients: microcrystalline cellulose, hydroxypropyl cellulose, croscarmellose sodium, sodium starch glycolate, magnesium stearate, FD&C Yellow #6/Sunset Yellow FCF aluminum lake, polyethylene glycol, talc, PVA, and titanium dioxide.

The placebo tablets match the active idelalisib formulations in appearance. The placebo tablets matching the 150-mg tablets are pink, film-coated, and include the following inactive ingredients: silicified microcrystalline cellulose, sodium starch glycolate, magnesium stearate, red iron oxide, polyethylene glycol, talc, PVA, and titanium dioxide. The placebo tablets matching the 100-mg tablets are orange, film-coated, and include the following inactive ingredients: silicified microcrystalline cellulose, sodium starch glycolate, magnesium stearate, FD&C Yellow #6/Sunset Yellow FCF aluminum lake, polyethylene glycol, talc, PVA and titanium dioxide.

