5.2.8. Overdose Precautions

In Phase 1 studies, an MTD for idelalisib was not reached when the drug was administered continuously at dose levels through 350 mg/dose BID (700 mg per day) {Coutre 2011, Kahl 2011}. However, in this protocol, an overdose is defined as administration of more than the prescribed daily dose (ie, >600 mg in a single day). In a subject who experiences an overdose consideration should be given as to whether idelalisib administration should be temporarily interrupted. If the overdose ingestion is recent and substantial, and if there are no medical contraindications, use of gastric lavage or induction of emesis may be considered. Observation for any symptomatic side effects should be instituted, and biochemical and hematological parameters should be followed closely (consistent with the protocol or more frequently, as needed). Appropriate supportive management to mitigate adverse effects should be initiated.

The Gilead Sciences medical monitor should be contacted if a study drug overdose occurs. Cases of study drug overdose will result in specific reporting requirements (see Section 8.8).

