5.3.4. Dose Levels

Study drug dose levels for Arm A and Arm B are described in Table 5-1. The lower dose level (Dose Level -1) is provided in case a subject requires a study drug dose modification.

Table 5-1. Study Drug Dose Levels

Treatment Arm	Starting Dose	Dose Level -1
Arm A	300 mg/dose BID	200 mg/dose BID
Arm B	150 mg/dose BID	100 mg/dose BID

Abbreviation: BID=twice per day

When the primary study (GS-US-312-0116) is stopped, and GS-US-312-0116 active study subjects become eligible for participation on Study GS-US-312-0117 subjects will be enrolled into Study GS-US-312-0117 at open label 150 mg BID. Subjects already participating in Study GS-US-312-0117 will remain on the same dose.

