8. SAFETY ASSESSMENTS

8.1. Adverse Event Definitions

8.1.1. Adverse Event

An adverse event (AE) is any untoward medical occurrence in a clinical study subject administered a pharmaceutical product which; does not necessarily have a causal relationship with study drug administration or usage. An adverse event can therefore be any unfavorable and unintended sign (including an abnormal laboratory finding), symptom, or disease temporally associated with the use of a medicinal product, whether or not considered related to the medicinal product. AEs may also include pre- or post-treatment complications that occur as a result of protocol specified procedures, lack of efficacy, overdose, drug abuse/misuse reports, or occupational exposure. Preexisting events that increase in severity or change in nature during or as a consequence of participation in the clinical study will also be considered AEs.

An AE does not include the following:

- Lymphocytosis
- Medical or surgical procedures such as surgery, endoscopy, tooth extraction, and transfusion. The condition that led to the procedure may be an adverse event and must be reported.
- Pre-existing diseases, conditions, or laboratory abnormalities present or detected before the screening visit that do not worsen
- Situations where an untoward medical occurrence has not occurred (e.g., hospitalization for elective surgery, social and/or convenience admissions)
- Overdose without clinical sequelae (see Section 5.2.8)
- Any medical condition or clinically significant laboratory abnormality with an onset date before the consent form is signed and not related to a protocol-associated procedure is not an AE. It is considered to be pre-existing and should be documented on the medical history CRF.

In this study, any of the following events will be considered an adverse event:

- Any complication that occurs as a result of a protocol-mandated procedure (eg, venipuncture, biopsy) in the screening, on-treatment, or post-treatment periods.
- Any pre-existing condition that increases in severity or changes in nature during or as a consequence of study drug administration. Worsening manifestations of the underlying cancer (eg, increase in pain, tumor flare reaction, tumor lysis syndrome) may be considered adverse events in this study.

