8.8. Special Situations Reporting Requirements

8.8.1. Definitions of Special Situations

Special situation reports include all reports of medication error, abuse, misuse, overdose, lack of effect reports and pregnancy reports regardless of an associated AE. Also includes reports of adverse reactions in infants following exposure from breastfeeding, and reports of adverse reactions associated with product complaints and reports arising from occupational exposure.

A pregnancy report is used to report any pregnancy following possible maternal or paternal exposure to the medicinal product.

Medication error is any unintentional error in the prescribing, dispensing, or administration of a medicinal product while in the control of the health care provider, subject, or consumer.

Abuse is defined as persistent or sporadic intentional excessive use of a medicinal product by a subject.

Misuse is defined as any intentional or inappropriate use of a medicinal product that is not in accordance with the protocol instructions or the local prescribing information.

An overdose is defined as an accidental or intentional administration of a quantity of a medicinal product given per administration or cumulatively which is above the maximum recommended dose as per protocol or in the product labelling (as it applies to the daily dose of the subject in question). In cases of a discrepancy in drug accountability, overdose will be established only when it is clear that the subject has taken the excess dose(s). Overdose cannot be established when the subject cannot account for the discrepancy except in cases in which the investigator has reason to suspect that the subject has taken the additional dose(s).

Lack of effect is defined as a situation where there is apparent failure of the medicinal product or medical technology to bring about the intended beneficial effect on the individual in a defined population with a given medical problem, under ideal conditions of use.

Product complaint is defined as complaints arising from potential deviations in the manufacture, packaging, or distribution of the medicinal product.

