1.3. Sample Size and Power

Planned Sample Size	Total of up to ~180 subjects (up to ~90 subjects per treatment arm)		
Power Statement	The sample size for this extension study is not based upon a formal statistical hypothesis. The upper bound of the sample size in this study is determined by the sample size of the preceding primary clinical trial (Study GS-US-312-0116). Assuming a $\sim 10\%$ dropout rate during Study GS-US-312-0116 and a further $\sim 10\%$ dropout rate in the transition from the primary study to the extension study, ~ 180 subjects are expected to be enrolled into Study GS-US-312-0117.		
Actual Enrollment and Impact on Power	 Actual enrollment: 161 subjects enrolled into Study GS-US-312-0117. Impact on power: Not applicable 		

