 - Baseline for efficacy and safety endpoints will be the first dosing of IDELA, unless otherwise specified.
 - In the analysis, the Study GS-US-312-0117 portion will include all the data collected on or after the first dosing date of IDELA. The Study GS-US-312-0117 portion may include data collected in Study GS-US-312-0116, if a subject switches to open-label IDELA in Study GS-US-312-0116 while waiting for the protocol amendment.
- Placebo in GS-US-312-0116 + IDELA 150 mg BID in GS-US-312-0117:
 - Includes subjects who experience IRC confirmed PD in Arm B of Study GS-US-312-0116 and subsequently enroll into Study GS-US-312-0117 to receive IDELA 150 mg BID during the double-blind portion of the study
 - Referred to 'Placebo+R (PD)/IDELA' throughout this SAP and the TFLs
 - Baseline for efficacy and safety endpoints will be the first dosing of IDELA, unless otherwise specified.
 - In the analysis, the Study GS-US-312-0117 portion will include all the data collected on or after the enrollment date of Study GS-US-312-0117.

Efficacy and safety data collected during the primary and extension studies will be presented in the following 3 treatment groups:

- IDELA+R (PD, non-PD)/IDELA
 - Includes all subjects who are randomized to Arm A in Study GS-US-312-0116 (ie, all subjects in IDELA+R/IDELA and IDELA+R (PD)/IDELA)
 - For those in IDELA+R (PD)/IDELA, only data collected in Study GS-US-312-0116 (ie, while taking IDELA 150 mg BID) will be included. For those in IDELA+R/IDELA, all the data collected across Study GS-US-312-0116 and GS-US-312-0117 will be included. By this summary, the efficacy and safety profile of IDELA 150 mg BID can be explored for subjects randomized to Arm A in Study GS-US-312-0116.

- Baseline for efficacy endpoints will be the date of randomization in Study GS-US-312-0116.
- Baseline for safety endpoints will be the first dosing of IDELA 150 mg BID in Study GS-US-312-0116.
- Placebo+R/IDELA
- Placebo+R (PD)/IDELA

Due to the small sample size (N = 4) for the IDELA + R (PD)/IDELA group, data collected from this group in Study GS-US-312-0117 (ie, while taking IDELA 300 mg BID) will only be presented in listings.

Baseline for each data summary is described in Table 3-1.

	Baseline for Disposition Summary		Baseline for Efficacy Summary		Baseline for Safety Summary
Treatment Group	312-0116	312-0117	All endpoints except for OS	OS	All endpoints

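### Protocol Section 5.2.8 fixes overdose at more than 600 mg a day, which matches the prescribed dose only on 300 mg BID and conflicts with Section 8.8.1

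*Protocol*

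**What the plan says.** Protocol Section 5.2.8 (Overdose Precautions) states that "an overdose is defined as administration of more than the prescribed daily dose (ie, >600 mg in a single day". It then lists what to do: consider interrupting idelalisib, consider gastric lavage or emesis after a recent and substantial ingestion, observe for symptoms, follow laboratory values closely, and contact the medical monitor. For reporting it refers to Section 8.8.

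Section 8.8.1, the definition used for special-situation reports, sets overdose against the maximum dose under the protocol or labelling, "as it applies to the daily dose of the subject in question".

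Section 5.3.4 (Table 5-1) gives starting doses of 300 mg BID in Arm A and 150 mg BID in Arm B, with reduced levels of 200 and 100 mg BID. It adds that once the primary study is stopped, "subjects will be enrolled into Study GS-US-312-0117 at open label 150 mg BID".

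Section 8.1.1 lists "Overdose without clinical sequelae (see Section 5.2.8") among the things that are not adverse events. For the meaning of overdose it therefore sends the reader to 5.2.8 and not to 8.8.1.

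**The concern.** The sentence in 5.2.8 gives a rule that depends on the subject's own dose and then, through the abbreviation for 'that is', equates it with one fixed number. Nothing in the protocol confines that number to Arm A, to 300 mg BID or to the blinded portion.

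At stake is whether the actions in 5.2.8 are started. A site that looks for a trigger finds a single figure, and for most dose levels that figure is too high. The gap is widest for subjects reduced to 100 mg BID because of toxicity. Section 5.4.4, for example, allows dosing to resume at 100 mg BID after Grade 4 neutropenia. No efficacy endpoint or analysis is affected.

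**Working it through.** **Inputs.** Dose levels come from Protocol Table 5-1. The 600 mg figure is from Protocol 5.2.8. Tablet strengths and counts are from Protocol 5.2.1 and 5.2.3. Enrollment is from SAP 1.3 and the size of the 300 mg BID group from SAP 3.5.1.

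**Step 1: reproduce the plan's figure.** Prescribed daily dose = 2 × mg per dose. For 300 mg BID, 2 × 300 = 600 mg. The figure reproduces at this level.

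**Step 2: repeat for each level.**

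| Level | Prescribed mg/day | 600 ÷ prescribed | Excess not flagged (600 − prescribed) |
|---|---|---|---|
| 300 mg BID (Arm A start) | 2 × 300 = 600 | 1.0 | 0 mg |
| 200 mg BID (Arm A reduced) | 2 × 200 = 400 | 1.5 | 200 mg |
| 150 mg BID (Arm B start, new open-label) | 2 × 150 = 300 | 2.0 | 300 mg |
| 100 mg BID (Arm B reduced) | 2 × 100 = 200 | 3.0 | 400 mg |

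The rule requires more than 600 mg, so an intake of exactly 600 mg is not flagged. The unflagged range therefore runs from just above the prescribed dose up to and including 600 mg.

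**Step 3: convert to tablets.**
- 150 mg BID, open label: 300 ÷ 150 = 2 extra tablets in a day.
- 100 mg BID in 100-mg tablets: 400 ÷ 100 = 4 extra tablets.
- 200 mg BID in 100-mg tablets: 200 ÷ 100 = 2 extra tablets.

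**Step 4: how many subjects could this concern?** SAP 1.3 records "161 subjects enrolled into Study GS-US-312-0117". SAP 3.5.1 describes the group that went on to 300 mg BID: "Due to the small sample size (N = 4"). By starting dose, at most 161 − 4 = 157 subjects (157 ÷ 161 = 97.5%) had a prescribed daily dose other than 600 mg.

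This is a ceiling. It includes blinded Arm B subjects, who took the same number of tablets as Arm A because each "will be provided with 1 tablet of active idelalisib and 1 tablet of placebo for oral administration at each dose". It also includes former placebo subjects, who under Section 5.1.2 "may delay initiation of idelalisib following enrollment on Study GS-US-312-0117 until the time of disease progression", and so may have started late or not at all. The documents do not give the actual number.

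**Step 5: compare the two definitions.** For an open-label subject on 150 mg BID who takes 450 mg in a day, Section 8.8.1 gives overdose (450 > 300). The verbal rule in 5.2.8 also gives overdose. The number in 5.2.8 does not (450 < 600).

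**The case against.** Four points can be made in defence of the text.

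- **The operative words are already correct.** Harm requires a site to ignore the verbal rule and use only the number. This stands as a limit on the claim: the text is a conflicting instruction, and nothing shows that events were missed.
- **Reporting is covered elsewhere.** Section 8.8 is subject-specific and separately makes medication error and misuse reportable, and Section 8.9.2 requires these reports within 24 hours. Section 8.1.1 excludes only overdoses without sequelae, so an untoward event after extra tablets is still an adverse event. This stands too. What remains exposed is the clinical-action text in 5.2.8.
- **The clinical risk is modest.** Section 5.2.8 reports no maximum tolerated dose through 350 mg BID (700 mg/day), and Section 5.10 describes only modest exposure gains above 150 mg BID. This limits the harm but does not correct the definition: 5.2.8 cites the tolerability finding and then sets a rule based on the prescribed dose anyway. Section 5.10 also notes that transaminase elevations may be more common at higher doses.
- **600 mg may be a blinded ceiling.** Sites did not know the dose, and at the starting level four 150-mg tablets hold at most 600 mg. This is a plausible origin, but the protocol does not state it. It does not cover open-label 150 mg BID. It also fails at the blinded reduced level in Arm A, where four 100-mg tablets are prescribed and six give exactly 600 mg, which is not above the limit. SAP 3.5.1 records that the primary study was stopped early and unblinded and that escalation to 300 mg BID was no longer offered, so open-label use is the case that now matters.

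**Conclusion.** Section 5.2.8 is wrong as written. Its only number fits one of the four prescribed dose levels and is 1.5 to 3.0 times the prescribed daily dose on the others. It contradicts both the words it is meant to explain and Section 8.8.1. The conclusion rests only on Table 5-1 and the two definitions, and needs no outside assumption.

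The consequence is limited to recognising overdose and starting the observation, laboratory follow-up and medical-monitor contact set out in 5.2.8. The count of 157 shows how widely the number misfits; it does not count overdoses or missed actions. This should be corrected because it is a safety trigger, although nothing in the efficacy analysis depends on it.

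**What to change.** In Section 5.2.8, replace the 600 mg parenthesis with limits tied to the subject's currently prescribed dose: more than 600 mg/day on 300 mg BID, 400 mg/day on 200 mg BID, 300 mg/day on 150 mg BID, and 200 mg/day on 100 mg BID. State that this is the same definition as in Section 8.8.1.

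For any subject still blinded, express the limit as more than 4 tablets a day. Both arms take 2 tablets per dose twice daily (2 × 2 = 4), so this rule does not reveal the arm.

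Deleting the parenthesis would remove the contradiction, but listing the limits gives sites a number they can use. The cost is one sentence of protocol wording, with no change to data collection or analysis.

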5.2.9. Inadvertent Exposure and Spill Precautions

Based on available data from nonclinical studies, idelalisib does not appear to be acutely toxic, genotoxic, or irritative at levels that are likely to result from inadvertent exposure to the contents of broken tablets. However, personnel handling the drug should use reasonable precautions to avoid eye contact, skin contact, inhalation, or ingestion of the study drug product. For further information regarding inadvertent exposure and spill precautions, please consult the idelalisib investigator brochure.

5.3. Study Drug Administration

5.3.1. Premedication

No specific premedications or supporting medications are required in conjunction with study drug administration.

5.3.2. Administration Instructions

The prescribed dose of study drug (idelalisib/placebo) should be taken orally. At each dose administration, the tablet number corresponding to the appropriate dose of study drug is to be swallowed whole with 100 to 200 mL (\sim 4 to 8 ounces) of water. In case of breakage of the tablets in the oral cavity, additional water should be taken as a rinse.

Study drug may be taken with or without food. There are no known dietary restrictions related to study drug use.

5.3.3. Dosing Schedule

Study drug should be taken on a BID schedule at approximately the same times each day. Ideally, doses should be taken at \sim 12-hour intervals (eg, at \sim 7 AM and at \sim 7 PM). While it is realized that variations in dosing schedule may occur in the outpatient setting, the prescribed regimen should be followed as closely as possible, especially in the clinic.

At specified clinic visits, the study drug will be administered in the clinic with dosing appropriately timed relative to blood sampling for idelalisib pharmacokinetics. As detailed in Section 6.2, clinic staff should record idelalisib administration information, including the exact clock time of each dose, for doses of study drug administered in the clinic or hospital. Thereafter, subjects will be given an adequate supply of tablets to take at home.

5.3.4. Dose Levels

Study drug dose levels for Arm A and Arm B are described in Table 5-1. The lower dose level (Dose Level -1) is provided in case a subject requires a study drug dose modification.

Table 5-1. Study Drug Dose Levels

Treatment Arm	Starting Dose	Dose Level -1
Arm A	300 mg/dose BID	200 mg/dose BID
Arm B	150 mg/dose BID	100 mg/dose BID

Abbreviation: BID=twice per day

When the primary study (GS-US-312-0116) is stopped, and GS-US-312-0116 active study subjects become eligible for participation on Study GS-US-312-0117 subjects will be enrolled into Study GS-US-312-0117 at open label 150 mg BID. Subjects already participating in Study GS-US-312-0117 will remain on the same dose.

